| Renal Artery Imaging  |   |   |                                 | X              |           |                    |      |      |      |      |       |    |   | X  | X  | (X)                      | (X)  |   |
| Blinding Assessment   |   |   |                                 |                            |           | X                  |      |      |      |      |       |    | X   |                | X              |                                      |                  |   |
| EQ-5D and SF-36   |   |   |                                 |                            | X         |                    |      |      |      |      |       |    | X   |                | X              | X                                    | X                | X |
| Mortality Assessment    |   |   |                                 |                            |           |                    |      | X    | X    |      | X     |    | X   |                | X              | X                                    | X                | X |
| Medication Review, Event Review   | All adverse events (AE) and medication review
After 12 months, previously reported AEs will need to be reviewed and updated as needed. |   |                                 |                            |           |                    |      |      |      |      |       |    |   |                |                | Serious AE and all medication review |                  |   |

1 DUS required as first line imaging modality at 6M. Repeat DUS, MRA, CT, or angiogram to be used if DUS is nondiagnostic. Renal angiography must be used if repeat DUS/CTA/MRA is nondiagnostic or stenosis >60-70% is suspected. The 6M DUS will not be required for subjects crossing over at 6M visit.

2 Conduct if follow-up missed.

3 If medically necessary, phone contact may be replaced with office visit. Office blood pressure (according to guidelines in Appendix L.7), only needs to be obtained if an office visit occurs.

4 Bicarbonate will not be measured for subjects enrolled in Japan and Europe.

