- **Enrollment (consent) to 12-months post procedure:** all medications and all adverse events
  - **12 to 36 months post-procedure:** all medications and serious adverse events only. Previously reported adverse events will be followed up through resolution until the end of the study.
- h) **Renal Artery Imaging** will be performed at the 6-month post-procedure visit to assess if a renal artery stenosis is suspected. A renal duplex ultrasound (DUS) will be obtained at 6M and submitted to the DUS Core Laboratory. If the DUS is determined to be nondiagnostic a repeat DUS, a MRA, CT or angiogram will be performed (repeat imaging is recommended to be completed within 30 days after confirmation of non-diagnostic imaging). If evidence of a clinically significant stenosis is indicated by the DUS or MRA/CT Core Laboratories, an angiogram must be obtained and submitted to the Angiographic Core Laboratory.
- A renal duplex ultrasound (DUS) at 6-month follow-up is not required for subjects randomized to the control group who are crossing over, if they are having the renal denervation procedure done within 30 days of their 6 month follow-up visit. If they are not having the renal denervation procedure done within the 30 days of their 6 month follow-up visit, a renal duplex ultrasound (DUS) is required.
  - The 12-month renal imaging will be required for all randomized subjects. If the renal imaging is determined to be nondiagnostic, a repeat DUS, MRA, CTA or angiogram will be performed. If repeat DUS, CTA, or MRA is nondiagnostic or evidence of a clinically significant stenosis ( $>60$ - $70\%$ ) is indicated, an angiogram must be obtained and submitted to the Angiographic Core Laboratory. Subjects who have already completed their 12-month visit follow up at the time of protocol approval will be required to undergo renal imaging at their next scheduled follow-up visit unless they have a renal angiogram due to crossover. For participating sites in Germany and the UK, only DUS or renal MRA imaging at the 12-month follow-up visit (or 24M or 36M follow-up as applicable) will be performed. For these countries, if the initial DUS or initial renal MRA is non-diagnostic, a repeat DUS or repeat renal MRA should be performed. If the initial imaging modality or subsequent repeat(s) are non-diagnostic, the investigator should choose the repeat imaging modality (DUS or MRA) that is expected to yield the required information for a diagnostic study.

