### H.3 Secondary Safety Objectives

The following secondary safety endpoints will be assessed:

- Acute/Procedural Safety Secondary Endpoints – Compared Between Groups at 1 Month Post-Procedure:
  - Significant embolic event resulting in end-organ damage
  - Renal artery perforation requiring intervention
  - Renal artery dissection requiring intervention
  - Vascular complications
  - End-Stage Renal Disease
  - $\geq 40\%$  decline in eGFR
  - New Myocardial Infarction
  - New Stroke
  - Renal artery re-intervention
  - Major bleeding according to TIMI definition (i.e. intracranial hemorrhage,  $\geq 5\text{g/dl}$  decrease in hemoglobin concentration, a  $\geq 15\%$  absolute decrease in hematocrit, or death due to bleeding within 7 days of the procedure)
  - Increase in serum creatinine  $> 50\%$  from Screening Visit 2
  - New renal artery stenosis  $> 70\%$ , confirmed by angiography and as determined by the angiographic core laboratory
  - Hospitalization for hypertensive crisis not related to confirmed non-adherence with medications or the protocol.
  
- Chronic Safety Secondary Endpoints – Compared Between Groups at 3, 6, 12, 24, and 36 Months Post- Randomization:
  - All-cause mortality
  - End-Stage Renal Disease
  - $\geq 40\%$  decline in eGFR

- New Myocardial Infarction
- New Stroke
- Renal artery re-intervention
- Major bleeding according to TIMI definition (i.e. intracranial hemorrhage,  $\geq 5\text{g/dl}$  decrease in hemoglobin concentration, a  $\geq 15\%$  absolute decrease in hematocrit, or death due to bleeding within 7 days of the procedure)
- Increase in serum creatinine  $> 50\%$  from Screening Visit 2
- Renal artery stenosis  $> 70\%$ , confirmed by angiography
- Hospitalization for hypertensive crisis not related to confirmed non-adherence with medications or the protocol.

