#### **Powered Primary Safety Endpoint**

Incidence of Major Adverse Events (MAE), defined as a composite of the following events, through one-month post-randomization (6 months for new renal artery stenosis)

- All-cause mortality
- End Stage Renal Disease (ESRD)
- Significant embolic event resulting in end-organ damage
- Renal artery perforation requiring intervention
- Renal artery dissection requiring intervention
- Vascular complications
- Hospitalization for hypertensive crisis not related to confirmed non-adherence with medications or the protocol
- New renal artery stenosis > 70%, confirmed by angiography and as determined by the angiographic core laboratory

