#### **Secondary Safety Endpoints**

Acute/Procedural Safety Secondary Endpoints - Compared Between Groups at 1 Month Post-Procedure:

- Significant embolic event resulting in end-organ damage
- Renal artery perforation requiring intervention
- Renal artery dissection requiring intervention
- Vascular complications
- End-Stage Renal Disease
- ≥40% decline in eGFR
- New Myocardial Infarction
- New Stroke
- Renal artery re-intervention
- Major bleeding according to TIMI definition (i.e. intracranial hemorrhage, ≥5g/dl decrease in hemoglobin concentration, a ≥15% absolute decrease in hematocrit, or death due to bleeding within 7 days of the procedure)
- Increase in serum creatinine > 50% from Screening Visit 2
- New renal artery stenosis > 70%, confirmed by angiography and as determined by the angiographic core laboratory
- Hospitalization for hypertensive crisis not related to confirmed non-adherence with medications or the protocol

Chronic Safety Secondary Endpoints – Compared Between Groups at 3, 6, 12, 24, and 36 Months Post-Randomization:

- Composite Safety Endpoint, defined as a composite of the following events:
  - All-cause mortality
  - End-Stage Renal Disease (ESRD)
  - Significant embolic event resulting in end-organ damage
  - Renal artery perforation requiring intervention
  - o Renal artery dissection requiring intervention
  - Vascular complications
  - Hospitalization for hypertensive crisis not related to confirmed non-adherence with medications and/or the protocol.
  - New renal artery stenosis > 70%, confirmed by angiography and as determined by the angiographic core laboratory
- All-cause mortality
- End-Stage Renal Disease
- ≥40% decline in eGFR
- New Myocardial Infarction
- New Stroke

- Renal artery re-intervention
- Major bleeding according to TIMI definition (i.e. intracranial hemorrhage, ≥5g/dl decrease in hemoglobin concentration, a ≥15% absolute decrease in hematocrit, or death due to bleeding within 7 days of the procedure)
- Increase in serum creatinine > 50% from Screening Visit 2
- New Renal artery stenosis >70%, confirmed by angiography and as determined by the angiographic core laboratory
- Hospitalization for hypertensive crisis not related to confirmed non-adherence with medications or the protocol

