#### 9.9.2. Secondary Safety Objectives

The following secondary safety endpoints will be assessed:

 Acute/Procedural Safety Secondary Endpoints – Compared Between Groups at 1 Month Post-Procedure:

- Significant embolic event resulting in end-organ damage
- Renal artery perforation requiring intervention
- Renal artery dissection requiring intervention
- Vascular complications
- End-Stage Renal Disease
- ≥40% decline in eGFR
- New myocardial infarction
- New stroke
- Renal artery re-intervention
- Major bleeding according to TIMI definition (i.e. intracranial hemorrhage, ≥5g/dl decrease in hemoglobin concentration, a ≥15% absolute decrease in hematocrit, or death due to bleeding within 7 days of the procedure)
- Increase in serum creatinine >50% from Screening Visit 2
- New renal artery stenosis >70%, confirmed by angiography and as determined by the angiographic core laboratory
- Hospitalization for hypertensive crisis not related to confirmed non-adherence with medications or the protocol
- Chronic Safety Secondary Endpoints Compared Between Groups at 3, 6, 12, 24, and 36 Months Post- Randomization:
  - Composite Safety Endpoint, defined as a composite of the following events:
    - All-cause mortality
    - End-Stage Renal Disease (ESRD)
    - Significant embolic event resulting in end-organ damage
    - Renal artery perforation requiring intervention
    - Renal artery dissection requiring intervention
    - Vascular complications
    - Hospitalization for hypertensive crisis not related to confirmed non-adherence with medications and/or the protocol
    - New renal artery stenosis >70%, confirmed by angiography and as determined by the angiographic core laboratory
  - ≥ 40% decline in eGFR
  - Increase in serum creatinine >50% from Screening Visit 2
  - New myocardial infarction
  - New stroke
  - Renal artery re-intervention
  - Major bleeding according to TIMI definition (i.e. intracranial hemorrhage, ≥5g/dl decrease in hemoglobin concentration, a ≥15% absolute decrease in hematocrit, or death due to bleeding within 7 days of the procedure)
  - Hospitalization for hypertensive crisis not related to confirmed non-adherence with medication and/or protocol.
  - Summary of health related Quality of Life (HRQoL) analysis based on reporting measures using accepted QoL instruments (EQ5D and SF36).

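### New renal artery stenosis is compared between arms at 1 month, and within the SAP's 3-month composite, although no renal scan is scheduled before 6 months; SAP 9.9.2 then omits the separate 6-month comparison.

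*SAP*

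**What the plan says.** **Early comparisons.** The acute list in SAP 9.9.2, headed "Compared Between Groups at 1 Month Post-Procedure", includes "New renal artery stenosis >70%, confirmed by angiography and as determined by the angiographic core laboratory". The acute list in SAP 5.2 has the same item ("New renal artery stenosis > 70%, confirmed by angiography and as determined by the angiographic core laboratory"). So do Protocol C.2 and H.3, the latter under "Acute/Procedural Safety Secondary Endpoints – Compared Between Groups at 1 Month Post-Procedure".

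**Later comparisons.** The chronic list in SAP 9.9.2 is headed "Compared Between Groups at 3, 6, 12, 24, and 36 Months Post- Randomization". It opens with an eight-part composite that includes stenosis, followed by separate rows. Stenosis has no separate row there, and neither do all-cause mortality or ESRD. SAP 5.2 has the composite and also separate rows for all three from 3 to 36 months. Protocol C.2 and H.3 have the separate rows and no composite.

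**Imaging schedule.** Protocol Tables 1 and 4 show an angiogram at the procedure and then nothing until "DUS required as first line imaging modality at 6M". Item h of Protocol F.7 agrees: renal artery imaging "will be performed at the 6-month post-procedure visit to assess if a renal artery stenosis is suspected". The 6-month window is days 166 to 194. Imaging at 12 months is required of all randomized subjects. At 24 and 36 months it applies only to those who passed their 12-month visit without a scan. The 6-month scan is waived for controls who cross over within 30 days of that visit.

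**Counting rule.** Under SAP 9.9.2 and Protocol H.3, a subject enters the denominator through an adjudicated event, or through a last contact beyond the lower limit of the visit window. A scan is not required. Out to 6 months, SAP 9.9.2 compares arms with Fisher's exact test and a two-sided 95% interval for the difference.

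**Primary safety endpoint.** SAP 5.1 treats stenosis differently from the other components: "through one-month post-randomization (6 months for new renal artery stenosis".

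**The concern.** A stenosis above 70% must be confirmed by angiography, and someone must first have a reason to order the angiogram. The plan's own trigger is the screening scan, which first takes place at 6 months. At 1 and 3 months the plan therefore tests a difference between arms in something that nobody has been scheduled to look for. Because contact alone makes a subject evaluable, not imaged is recorded as no event.

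At 6 months, when scans exist and controls have not yet crossed over, the chronic list in 9.9.2 gives no separate stenosis comparison. Protocol J.2 names renal artery narrowing from the procedure or the RF energy as a potential risk, so readers will look for this row. As written, 9.9.2 gives them a 1-month row with no screening behind it and no separate 6-month row.

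**Working it through.** **1. Reproduce the plan's own stenosis figure.** SAP 9.9.2.1 gives an exact 95% interval of (0.6%, 8.5%) for 3/100. The Clopper-Pearson limits are the 2.5% quantile of Beta(3, 98) = 0.62% and the 97.5% quantile of Beta(4, 97) = 8.52%. The stated interval is correct.

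**2. Set the analysis against the schedule.**

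| Time point | Scheduled renal imaging | Stenosis in SAP 9.9.2 | Stenosis in SAP 5.2 |
|---|---|---|---|
| 1 month | none | separate row | separate row |
| 3 months | none | composite only | composite and separate row |
| 6 months | duplex ultrasound | composite only | composite and separate row |
| 12 months | all randomized subjects | composite; descriptive rate in 9.9.2.1 | composite and separate row |
| 24 and 36 months | only if the 12-month scan was not done | composite only | composite and separate row |

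**3. What the 1-month row would look like.** Protocol B.1.2 gives 166 randomized to denervation and 165 to sham. With no scheduled scan and no clinically detected case, and assuming everyone has the required contact, the row is 0/166 vs 0/165 and Fisher p = 1.00. To show how such zeros can be read, the exact two-sided 95% upper limit for one arm is 1 − 0.025^(1/166) = 2.2%. That is below the 3.1% that SAP 9.9.2.1 expects at 12 months, yet no subject need have been scanned. The plan calls for an interval for the difference, so this per-arm limit is an illustration and not a planned output.

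**4. What the same zeros would mean if everyone were scanned.** At a true rate of 3.1%, 166 subjects would yield 0.031 × 166 = 5.1 expected cases. The chance of seeing none would be (1 − 0.031)^166 = 0.5%. So zero in a scanned arm is informative, and zero in an unscanned arm is not. The 3.1% is the SAP's 12-month figure, stated there without a severity threshold, and is used only as a benchmark.

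**5. Effect of the contact-based denominator.** If only scanned subjects can be found to have a stenosis, the reported rate is roughly the true rate times the fraction scanned. The fractions below are assumptions:

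- 85% scanned: 0.031 × 0.85 = 2.6%
- 50% scanned: 0.031 × 0.50 = 1.6%
- 0% scanned: 0%

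This dilution also applies at 6 months. There the waiver for controls who cross over falls on one arm only, so it can distort the comparison as well as lower the rate.

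**6. Is the 6-month comparison supplied elsewhere in the SAP's analysis sections?** SAP 9.9.2.1 is descriptive, covers 12 months only and names no comparison between arms. SAP 9.9.9 promises long-term imaging analyses without specifying them. Neither fills the gap in the 9.9.2 list.

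**The case against.** The strongest reply has four parts.

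*Stenosis is not dropped.* A reader of 9.9.2 alone might infer that the SAP abandons stenosis as an endpoint once scans begin. The documents do not support that. SAP 5.2 and Protocol C.2 and H.3 keep a separate row from 3 to 36 months, and 9.9.2.1 reports 12-month stenosis by itself. Mortality and ESRD lose their separate rows in 9.9.2 too, so this looks like list drafting and not a choice about stenosis. That stands, but it does not remove the conflict. Hospitalization for hypertensive crisis is also in the composite and keeps its separate row in the same list. SAP 9.13 declares no change to the planned analysis, and SAP 10 requires independent validation of these endpoints. Programmers working from 5.2 and from 9.9.2 would build different tables.

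*Early stenosis is not undetectable.* One might infer that the 1- and 3-month counts must be zero. They need not be. Creatinine is drawn before discharge, at 4 weeks and at 3 months, and clinically driven angiography can confirm a stenosis at any time. The accurate statement is that subjects are not systematically screened. For this reason the early counts should be relabelled and kept visible.

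*Most of the 3-month composite is sound.* Its other components do not depend on a scheduled renal scan. This stands; the composite needs a label, not removal.

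*The change comes late.* Protocol B.1.2 reports that enrollment has stopped and that no major safety events were reported at 1 month. This argues against erasing a pre-specified row and for recording the change openly.

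**Conclusion.** The point holds in a limited form. Stenosis is compared between arms at 1 month and within the SAP's 3-month composite with no scheduled imaging behind it, and the contact-based denominator counts unscanned subjects as event-free. In addition, 9.9.2 disagrees with SAP 5.2 and Protocol H.3 and provides no separate between-arm stenosis comparison at 6 months.

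A reader might infer that the trial's safety conclusion is at risk. The documents do not support that: the primary safety endpoint gives stenosis a 6-month window, so the 1-month timing problem does not reach it. What is affected is how secondary safety results are reported and read. The likely early result, 0/166 vs 0/165 with p = 1.00, would say almost nothing about stenosis. This assumes that few or no subjects are imaged for clinical reasons before 6 months; the documents do not say how many were.

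**What to change.** 1. At 1 and 3 months, remove the between-arm stenosis test (SAP 5.2 and 9.9.2, Protocol C.2 and H.3). Show any stenosis as a count labelled *clinically detected only, no scheduled imaging*, and label the 3-month composite the same way. A real early event then stays in the tables.
2. Restore stenosis as a separate between-arm row in the 9.9.2 chronic list from 6 months, aligned with SAP 5.2.
3. For that row, use as denominator the subjects with diagnostic renal imaging, or a confirmed event, by the time point. Report the number imaged per arm. Flag controls whose 6-month scan was waived for crossover, and state whether their crossover angiogram counts as imaging. State also how a 6-month scan done after day 180 is counted, since the counting rule's example stops at day 180 and the visit window runs to day 194.
4. Label 24- and 36-month rates in non-crossover subjects as cumulative, resting mainly on the 6- and 12-month scans.

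Record these as changes under SAP 9.13, noting that 1-month results were already known. The cost is wording and some table programming, smaller stenosis denominators, and the loss of the 1-month test and of the separate 3-month test listed in SAP 5.2 and the protocol. No new scans or subjects are needed.
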